## 14.4. **RETREATMENT WITH PVSRIPO**

The analysis of data collected in conjunction with PVSRIPO retreatment will be descriptive as the sample size is expected to be limited. The rigor and approach to all the associated exploratory analyses will be dependent upon the number of patients who are retreated.

The toxicity associated with the second infusion of PVSRIPO will be summarized separately from those observed with the first infusion, but in a similar manner. A landmark survival analysis will describe PFS and OS starting at the time of the second infusion. Changes over time after the first infusion of PVSRIPO in various immune function/response parameters will be described. Among patients who receive a second PVSRIPO treatment, changes observed in immune function/response associated with the second infusion will be compared to those observed with the first infusion.

# 15. POTENTIAL BENEFITS AND RISKS

## **15.1. POTENTIAL BENEFITS**

The potential benefits may include reduction and/or remission of the subject's brain cancer. Because this procedure is experimental, it cannot be guaranteed that subjects will receive any benefit as a result of participating in this research study. The information collected in this research may help scientists better understand the mechanisms involved in viral oncolysis. If such an understanding emerges from this research, it may benefit society by furthering the development of improved treatment methods for WHO grade IV malignant glioma in the future.

## **15.2. POTENTIAL RISKS**

#### 15.2.1. Surgical Complications

The stereotactic catheter implantation procedure carries a risk for loss of neurologic function, non-neurologic complications and death. These risks depend primarily on the preoperative condition of the patient, the size and location of the tumor and associated diseases. The potential risk for the patient will be discussed in detail with the patient and family.

#### 15.2.2. Anesthesia

Patients undergoing general anesthesia may be subjected to associated risks including pneumothorax, pneumonia, airway injury, hypotension, myocardial infarction, stroke, hepatic and renal injury and death.

#### 15.2.3. Poliomyelitis

PVSRIPO has been tested in NHPs according to the WHO standardized monkey neurovirulence tests. These tests revealed the absence of neuropathogenic properties, evident as failure to induce symptoms of poliomyelitis in NHPs after intracerebral inoculation of virus. However, PVSRIPO are replication-competent viral agents that, in principle, retain the potential to cause motor neuron damage. Possible complications include transient or permanent mono- or paraparesis, paralysis, and life-threatening respiratory insufficiency.

#### 15.2.4. Virus Recombination and Mutation

PVSRIPO retains the ability to alter its genome during replication upon administration to patients. Various mechanisms are known to lead to genetic adaptation, including spontaneous mutagenesis and recombination that may give rise to viral progeny with changed properties. Empirical studies in tissue culture and laboratory animals demonstrated that prolonged passaging in GBM cells does not select for genetic changes in viral progeny. However, the occurrence of such events cannot be categorically excluded in patients receiving intracerebral PVSRIPO. Genetic changes may cause an altered phenotype of PVSRIPO, including adaptation to improved virus replication in the normal CNS.

#### 15.2.5. Long-Term Sequelae of Virus Injection

PVSRIPO does not encode foreign genetic material, polioviruses are unable to insert viral genetic material in the host genome and polioviruses are incapable of inducing latent or chronic CNS infection. Therefore, PVSRIPO is unable to induce long-term expression of foreign polypeptides or long-term persistence of virus replication. Thus, there are no long-term neurologic consequences to intracerebral PVSRIPO administration in study subjects. For these reasons, no specific measures to analyze the potential for persistence of virus replication in the CNS of long-term survivors are indicated.

Prolonged gastrointestinal propagation of polioviruses, associated with prolonged virus shedding with stool, has been reported in select individuals with acquired or rare inherited immunodeficiency disorders. Primate toxicology results indicate that extraneural dissemination and shedding of PVSRIPO with stool do not occur after intracerebral inoculation. However, if PVSRIPO shedding is detected in stool samples scheduled to be collected from study subjects, virus excretion will be analyzed and documented in study subjects at monthly intervals as long as it persists.

#### 15.2.6. Gastrointestinal Infection and Virus Excretion

After oral uptake, poliovirus replicates in the gastrointestinal tract and is excreted by infected individuals with stool. Gastrointestinal viral replication usually is asymptomatic, but may cause mild symptoms of gastrointestinal discomfort. Tests of PVSRIPO in NHPs suggest that excretion of virus does not occur after intracerebral administration, implying the absence of gastrointestinal replication. However, PVSRIPO excretion with stool cannot be categorically excluded in patients enrolled in this study.

#### 15.2.7. Cerebral Edema and Increased Intracranial Pressure

Cerebral edema may be secondary to the disease process itself, the surgical procedure, necrosis from previous radiation, or inflammation due to immune infiltration of the brain or destruction of tumor cells. Symptoms may include, but are not limited to, severe headache,

confusion, lethargy, unresponsiveness, coma, or focal neurological deficits. Patients will be monitored throughout the course of the study and upon any signs or symptoms of cerebral edema, may have their steroid doses increased or receive treatment with an osmotic diuretic, or surgical decompression. Edema that fails to respond to aggressive therapy may lead to permanent neurological impairment. The probability of this risk can be predicted to some degree based upon tumor size, location, pre-operative neurological impairment, and post-operative course prior to virus administration.

**Special consideration:** In the event a patient demonstrates neurologic or radiographic signs suggestive of an inflammatory reaction secondary to the immune response expected from PVSRIPO for which it would be considered to increase dexamethasone above 4 mg a day after the first 2 weeks post PVSRIPO infusion, dexamethasone will not be increased any further. Instead, patients will be initiated on bevacizumab 7.5 mg/kg IV every 3 weeks and imaged with an MRI after 3 doses (every 9 weeks +/- 2 weeks) to assess if continued utilization of bevacizumab to control the cerebral inflammation is needed. Bevacizumab will not be provided by the study. Every attempt should be made to discontinue dexamethasone. Once patients start bevacizumab, the follow-up visit schedule will be adjusted to coincide with the timing of the bevacizumab instead of the prior PVSRIPO infusion. Therefore, patients will return approximately every 9 weeks for an evaluation with MRI.

If there are adverse events or other circumstances prohibiting the use of bevacizumab, we will use corticosteroids or surgery, or other interventions deemed more appropriate for the patient by the treating physician, if needed, to treat the inflammatory reaction secondary to PVSRIPO.

#### 15.2.8. Risk of Infection

The intracerebral catheter placement and infusion may include the risk of infection. However, similar procedures including stereotactic biopsy and ventriculostomy placement are commonly used in the routine clinical care of patients with malignant brain tumors with a very low and acceptable rate of infection. In the most extreme situation, however, infection may lead to systemic bacterial/fungal sepsis and possibly death. The risk of infection will be minimized though by performing catheter implantations in the Operating Room. Patients will be monitored throughout the course of the study for any signs and symptoms of infection. If an active infection is suspected, patients will be cultured and treated with appropriate antibiotics.

#### 15.2.9. Risks of Phlebotomy

Drawing blood or inserting an intravenous catheter into an arm vein may result in bruising or swelling in the area of the insertion, bleeding at the site of the needle puncture, light headedness, fainting and very rarely, local infection, which may be severe. These risks are reduced by the fact that the blood will be drawn by a qualified physician, nurse or phlebotomist (a professional trained to draw blood).

#### 15.2.10. Risks of MRI

Risks and/or discomforts associated with MRI scans include anxiety produced from being in a tight, enclosed space (claustrophobia). In addition, the machine operates using a large and powerful magnet, which attracts certain metals. Therefore, people with these metals in their bodies (specifically pacemakers, infusion pumps, metal aneurysm clips, metal prostheses, joints, rods or plates) will be excluded from the study. Patients will also be checked to make sure that they do not bring any metal objects into the MRI facility. Dental fillings are less affected by the magnetic fields generated and are therefore permitted. It will be asked that patients let the physicians conducting this study know of any metal in their bodies other than dental fillings.

## 15.2.11. Allergic Reactions to Contrast Agents

During the MRI, patients will be given a contrast agent. The agent is given routinely to obtain enhanced MRI scans of the brain. The agent is administered through the vein and requires the placement of an IV catheter. The catheter placement is similar to drawing blood except that the catheter remains in the vein during the time the agent is actively delivered. The risks of a blood draw and insertion of a catheter are similar. There have been a few, rare cases of allergies to the agent used in MRI contrast enhanced scans. Patients with any known severe allergies to contrast agents will be excluded from the study. Patients with mild allergies (i.e., rash only) will be pretreated with Tylenol and Benadryl prior to injection of the contrast agent. In addition to the gadolinium (contrast agent) being given for MRI contrast, it will also be co-infused with the study drug to assess infusion distribution. It is not FDA approved for gadolinium to be administered in this way. The potential risks of intracerebral infusion of gadolinium contrast agents are not completely known but are believed to be small. Risks for infusion of gadolinium contrast agents intrathecally for procedures such as cistemography have been somewhat better studied, and were recently summarized by Selcuk et al (2009) (50). Encephalopathy, coma and seizures have been reported as side effects in case reports of accidental administration of large amounts of gadolinium contrast agents intrathecally in humans (51, 52). When these contrast agents are used in appropriately low dose, however, the risk of intrathecal administration appears reasonably low. No neurological sequelae attributable to the procedure were detected in any patients in one year follow-up of series of 85 patients (50) and 95 patients (53), or in any of 51 patients after over 4 years of mean follow-up in another (54). Although these results cannot be extrapolated to the procedure proposed in the current research, they indicate that direct exposure of the brain to small amounts of gadolinium contrast agent is generally well tolerated.

A rare but serious adverse reaction has been observed in patients that received a gadolinium-based contrast material during MRI examinations, a reaction called nephrogenic systemic fibrosis (NSF). Patients with kidney disease are at increased risk of developing NSF. NSF may cause skin thickening, joint pain and/or swelling. In rare cases NSF can lead to lung and heart problems and cause death.

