	
 
Able to undergo brain MRI with and without contrast.
 

Exclusion	Because of the unknown risk of virus administration potentially affecting a
Criteria:	developing fetus or growing infant, females who are pregnant or breast-
	feeding will be excluded. Adults of reproductive potential not employing an
	effective method of birth control will be excluded. Sexually active women of
	child bearing potential, whose partner is male, must use medically accepted
	birth control. Sexually active men, whose partner is a female of child bearing potential, must use a medically accepted birth control.
	
 
Patients with an impending, life-threatening cerebral herniation syndrome,
 

	
 
Patients with an impending, methodatening cerebral hernation syndrome, based on the assessment of the study neurosurgeons or their designate, will be excluded.
 

	Because the potential toxicities from the agent being studied in this protocol
	may be similar to some known diseases or may be more dangerous in the context of certain known diseases, the following patients will be excluded:
	
 
Patients with an active infection requiring intravenous treatment or having an unexplained febrile illness (Tmax > 99.5 F/37.5 C),
 

	
 
Patients with known immunosuppressive disease or known human immunodeficiency virus infection,
 

	
 
Patients with unstable or severe intercurrent medical conditions such as
 

	severe heart (New York Heart Association Class 3 or 4) or known lung
	(FEV 1 < 50%) disease, uncontrolled diabetes mellitus,
	
 
Patients with albumin allergy,
 

	
 
Patients with Gadolinium allergy.
 

	Patients with a previous history of neurological complications due to poliovirus
	infection will be excluded.
	
 
Patients who have not recovered from the toxic effects of prior chemo- and/or radiation therapy will be excluded. Guidelines for this recovery period are dependent upon the specific therapeutic agent being used.
 

	
 
Patients may not have received chemotherapy or bevacizumab ≤ 4 weeks
 

	[except for nitrosourea (6 weeks) or metronomic dosed chemotherapy such
	as daily etoposide or cyclophosphamide (1 week)] prior to starting the study
1	drug unless patients have recovered from side effects of such therapy.

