Study Design:	This protocol is designed primarily to determine the MTD and DLT of a novel oncolytic viral recombinant with GBM-specific viral translation, replication and cytotoxicity. PVSRIPO will be delivered intratumorally by convection-enhanced delivery using an intracerebral catheter placed within the enhancing portion of the tumor. To enable tracking of the inoculum, 1 mM Gadolinium will be co-infused. The contrast agent (Gd-DTPA) will be added to the virus-containing infusate. Based on pre-clinical toxicity studies in non-human primates, the starting amount of the agent to be delivered will be 1 x 10  tissue culture infectious dose (TCID50). Due to limitations imposed by manufacture and dosing volume in Cynomolgus macaques, the MTD was not reached in non-human primates. Intra-thalamic inoculation of 5 x 10  TCID in Cynomolgus macaques did not cause any toxicity. A total of 3 mLs of the agent in physiologic saline stabilized with 0.2% human serum albumin will be delivered over approximately 6 hrs 30 minutes, corresponding to a flow-rate of 0.5 mL/hr. The agent is stable at room temperature during the intended instillation period and the intended delivery apparatus is not associated with adsorptive loss of PVSRIPO. PVSRIPO dose escalation will be accomplished by increasing agent concentration allowing flow-rate and infusion volume to remain constant.
	A two-step continual reassessment method design will be used for dose escalation. Starting at dose level 1, one patient will be treated at each dose level. Decisions concerning dose escalation for subsequent patients will be based upon the occurrence of DLT during the first 4 weeks after treatment administration. Initially,

each patient will be observed for  $\geq$  4 weeks before the next patient is treated. If no patients experience a DLT on the first 4 dose levels, all subsequent patients will be treated at dose level 5. Escalation will be interrupted if any of the patients assigned to one of the first 4 dose levels or  $\geq$  20% of patients treated at dose level 5 experience a DLT. In that case, further dose escalation or de-escalation will be guided by the likelihood-based implementation of the continual reassessment method. Greater detail is provided in section 11.1.5.1.

Historical Modifications to the Protocol:

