#### 9.2.3. Medical Conditions

Because the potential toxicities from the agent being studied in this protocol may be similar to some known diseases or may be more dangerous in the context of certain known diseases, if the patients meet any of the following they will be excluded:

- Active infection requiring intravenous treatment or having an unexplained febrile illness (Tmax > 99.5 F/37.5 C).
- Known immunosuppressive disease or known human immunodeficiency virus infection.
- Unstable or severe intercurrent medical conditions such as severe heart (New York Heart Association Class 3 or 4) or known lung (FEV1 < 50%) disease, uncontrolled diabetes mellitus.
- Albumin allergy. Albumin is added to the agent as a stabilizer. Patients with a known allergy will be excluded.
- Gadolinium allergy. Gadolinium is used as contrast for the MRI.

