#### Figure 2. Genetic structure of PVSRIPO

PVSRIPO is formulated in 50 mM sodium phosphate in 0.9% sodium chloride, pH 7.4 with 0.2% human serum albumin. It is provided in sterile, single use containers. PVSRIPO must be stored at less than or equal to -70°C. Once thawed, it is a clear colorless liquid with no evidence of particulates or foreign matter. PVSRIPO was manufactured at the Biopharmaceutical Development Program/SAIC-Frederick at NCI-Frederick. For tracking intratumoral/intracerebral distribution of the inoculum, the study agent suspension will be supplemented with gadolinium-DTPA diamide (Magnevist®) at a final concentration of 1 mM. Magnevist® is stored at room temperature.

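### Gadolinium allergy of any severity is an exclusion in the synopsis and section 9.2.3, but section 15.2.11 keeps patients with a rash-only allergy in the study.

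*Combined protocol and SAP*

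**What the plan says.** Three places in the combined protocol and SAP deal with this allergy.

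- The synopsis lists among its exclusions "Patients with Gadolinium allergy", with no qualifier.
- Section 9.2.3 opens its list of medical conditions with "if the patients meet any of the following they will be excluded" and includes "Gadolinium allergy. Gadolinium is used as contrast for the MRI". It gives no severity limit.
- Section 15.2.11, in the chapter on risks, says "Patients with any known severe allergies to contrast agents will be excluded from the study" and then "Patients with mild allergies (i.e., rash only) will be pretreated with Tylenol and Benadryl prior to injection of the contrast agent".

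Gadolinium reaches the patient by two routes. Section 15.2.11 says so itself: "In addition to the gadolinium (contrast agent) being given for MRI contrast, it will also be co-infused with the study drug to assess infusion distribution". The study design part of the synopsis gives the concentration: "To enable tracking of the inoculum, 1 mM Gadolinium will be co-infused". Section 10.1 repeats the final concentration of 1 mM. Section 15.2.11 adds that giving gadolinium in this way is not FDA approved, and that its risks are incompletely known though thought to be small.

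**The concern.** An exclusion criterion should give one answer for one patient. Here a patient with a known rash-only reaction to gadolinium gets opposite answers, depending on which section the study team reads.

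What is at stake is more than whether a scan is done with contrast. Enrolment also means gadolinium delivered into the tumour. The premedication in 15.2.11 is attached to the contrast injection, which that section has just described as intravenous. It does not mention the infusion. A team relying on 15.2.11 could treat someone whom section 9.2.3 makes ineligible, and under section 16.6 one ineligible subject is enough for an unsatisfactory monitoring rating.

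**Working it through.** The plan gives no figure to reproduce, and no sample size, error rate or power depends on this point. The check is a comparison of the current text.

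**1. Are the sections about the same agent?** Yes. Section 15.2.11 begins with contrast agents in general, but it concerns the MRI agent and goes on to name it as gadolinium.

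**2. Are they about the same patients?** Yes. In 15.2.11 the sentence on mild allergy directly follows the one excluding known severe allergies. The two read most naturally as a severe/mild split of allergy already known at screening, and not as instructions for a reaction that first appears on study.

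**3. The answers side by side:**

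| Known gadolinium allergy | Synopsis and 9.2.3 | 15.2.11 |
|---|---|---|
| Severe | Excluded | Excluded |
| Mild, rash only | Excluded | Allowed, premedicated before the contrast injection |

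Only the second row conflicts.

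**4. Does another criterion settle it?** Inclusion criterion 9.1.8 requires that the patient can have brain MRI with and without contrast. It does not mention allergy, and a premedicated patient could arguably meet it. It is also not among the inclusion criteria that 11.2.1 carries over to retreatment (9.1.2 to 9.1.4).

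**5. What would an admitted patient receive in the infusate?** Section 11.1.2 gives a delivered volume of 3 mL, and the synopsis and section 10.1 give 1 mM:

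0.003 L × 1 mmol/L = 0.003 mmol = 3 micromol of gadolinium, nominally, over about 6.5 hours.

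This describes the exposure. It is not evidence of harm.

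**6. What does the plan provide at infusion?** Section 11.1.2 has epinephrine and diphenhydramine available, neurologic status, oxygen saturation and cardiac rhythm monitored, and the infusion given in the intensive care or step-down unit. It also assigns the management of acute reactions to the study drug to those units. These are measures for responding to a reaction. None is an eligibility rule or a premedication for known allergy.

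**7. Who can still be affected?** Section 16.6 puts the closure of enrolment to new subjects at June 2017, with selected patients still being retreated. Section 11.2.1 applies exclusions 9.2.1 to 9.2.10 to retreatment. These patients are at least 12 months past a first infusion that contained gadolinium, and Table 5 schedules repeated MRIs in that time. A mild reaction could come to light in that interval. The two sections would then disagree about the second infusion.

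**The case against.** The strongest reply is that section 9 plainly governs. The synopsis sends the reader there for eligibility, 11.2.1 cites its exclusions by number for retreatment, and 15.2.11 only describes risks. Section 16.4 requires an eligibility checklist, and section 16.6 reports that the eligibility of all enrolled subjects was monitored from September 2013. Much of this stands, and it makes a wrong enrolment unlikely. It does not remove the conflict, because 15.2.11 states an exclusion rule of its own and no clause gives either text precedence.

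The second reply is that almost nobody is left to be affected. That also stands. New enrolment is closed, and retreatment candidates have already had gadolinium by the intracerebral route once.

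A reader might also infer two stronger things that the documents do not support:

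- **That a reaction during infusion would go unmanaged.** Section 11.1.2 provides emergency drugs, monitoring and acute-reaction care. Only premedication for the infusion is unstated.
- **That a gadolinium reaction would automatically be counted as PVSRIPO toxicity.** Section 16.5 requires each event to be categorised by its relationship to treatment. Contrast reactions are not among the listed exceptions in 11.4.1, so a sufficiently serious one might be counted under the monitoring in 11.5. A rash that resolves would not be expected to meet that definition.

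**Conclusion.** The inconsistency is real, in current text, and minor. For one narrow group, patients with a known rash-only gadolinium allergy, the synopsis and 9.2.3 say excluded and 15.2.11 says allowed. It affects eligibility and exposure to co-infused gadolinium. It does not touch any endpoint, analysis or sample size.

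The size cannot be expressed as a number of patients, because the documents give no prevalence of such allergy. Nothing in them shows that an allergic patient was ever enrolled, and it would go too far to infer that every rash-only patient was treated.

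The conclusion rests on two readings: that the mild-allergy sentence refers to allergy known beforehand, and that section 9 in practice controls enrolment. If the sentence referred only to reactions arising on study, the conflict would largely fall away, but its place directly after the exclusion of known severe allergy tells against that.

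**What to change.** Reconcile section 15.2.11 with section 9.2.3 and the synopsis so that all three state one eligibility rule for gadolinium allergy. Make the rule say explicitly that it covers both the intravenous MRI contrast and the gadolinium in the infusate, and that it applies to retreatment through 11.2.1. Which rule is adopted is a clinical decision for the investigators, and this review takes no position on it.

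Mentioning the co-infusion in the rationale printed under 9.2.3 would be a helpful editorial addition but is not needed to remove the contradiction.

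The cost is a wording amendment. The consent form was not available to this review, so whether it needs a matching edit should be checked. At most a very few retreatment candidates would see their eligibility clarified, and no analysis changes.
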